6.4 Biomarker Sample Collection

6.4.1 Blood

Blood samples for COHb in whole blood (2 x 4 mL), sICAM in plasma (1 x 4 mL), WBCs in whole blood (measured in hematology sample), HDL-C in serum (1 x 3.5 mL), MCP-1 in serum (1 x 3.5 mL), and serum for bio-banking (up to 17 mL) will be collected during Test Visits 1, 3, and 5. Samples for COHb will be collected in the afternoon and samples for the other biomarkers and bio-banking will be collected following an overnight fast of at least 8 hours.

Up to approximately 118 mL of blood will be required for the planned assessments during the entire study.

Detailed instructions for collection, processing, and shipping of blood samples will be provided separately.

6.4.2 Urine

24-hour urine collections for biomarker measurements will take place during Test Visits 1, 3, and 5. Each 24-hour urine collection will begin at a time following check-in and will end at the same time \pm 30 minutes the following day.

Subjects will be instructed as to urine collection methods. Subjects will be instructed to attempt to void prior to the beginning and at the end of each interval. All urine must be collected during the entire 24-hour interval. The start and stop time of each 24-hour interval and the total weight of the collection will be documented. The weight of the 24-hour urine collection containers will be documented prior to the collection (tare weight) and following completion of the collection.

Urine will be refrigerated during the collection interval. Collections for each subject will be pooled periodically into one labeled container throughout the interval and the total weight (g) will be measured and recorded at the end of the 24-hour interval. Any missed voids will be documented, including the reason for missing. Aliquots will be prepared as noted in the following chart.

At the discretion of the site, 24-hour urine collection during Test Visits 3 and/or 5 may be completed by subjects at home. Subjects will be provided the materials required and will be instructed on the at-home urine collection method.

Page 68 CA22747_PROTOCOL AMENDMENT 3_24MAR2020

Biomarker	Number of Aliquots/ Volume Required	Container Type
Nicotine equivalents	2 aliquots of 5 mL each	polypropylene
1-OHP		
8-epi- PGF2α		
11-DHTXB2		
Creatinine (for adjustment)		
NNAL / NNN	2 aliquots of 10 mL each	UV shielded
MHBMA	_	polypropylene
3-HPMA / CEMA / HMPMA		
S-PMA		
HEMA		
1-AN / 2-AN		
o-tol		
3-OH-B[a]P		
Bio-banking	2 aliquots of 300 mL each	polypropylene

All aliquots will be prepared within 120 minutes from end of the collection and will be stored at $-20 \pm 10^{\circ}$ C until shipped for analysis.

Detailed instructions for collection, processing, and shipping of urine samples will be provided separately.

6.5 Physiologic Assessments

6.5.1 Fractional Concentration of Exhaled Nitric Oxide

FeNO will be measured using a Niox Vero (or similar device) during Test Visits 1, 3, and 5.

FeNO measurements will be preceded by a 30-minute (minimum) abstention from study product use. Water and food intake should be restricted for 1 hour prior to measurement. Subjects will be requested to rinse their mouths with water prior to the procedure.

6.5.2 Blood Pressure and Heart Rate

Blood pressure (systolic and diastolic) and heart rate measurements for physiologic assessment purposes will be taken from the Test Visit 1, 3, and 5 check-in vital signs measurements.

6.6 Subjective Measures

The PSCDI/PSECDI, Cough Questionnaire, QSU-Brief, MTWS-R, PES, Product Liking Questionnaire, Future Intent to Use Questionnaire, and Product and Health Effect Perceptions Questionnaire will be completed during Test Visits 1, 3, and 5, as applicable, using an electronic device.

All relevant software and staff training specific to the electronic questionnaires will be provided.

All subjective measures questionnaires are provided in the Appendices 3 - 10.

At the discretion of the site, some or all questionnaires during Test Visits 3 and/or 5 may be completed by subjects at home. Subjects will be provided the materials required and will be instructed on the at-home questionnaire completion.

6.7 Nicotine Pharmacokinetics Assessments

6.7.1 Product Use

Product use for the PK assessments will consist of two sessions of use of the assigned study product (Day 1 for the continue-smoking and JUUL[®] arms, Day 5 for the *my*bluTM arm). The first session will be performed in the morning following an abstention from product use of at least 10 hours and will consist of a fixed puffing regimen of 10 puffs taken at 30-second intervals. Puff duration will be 3 seconds for the e-cigarette products and as desired for the combustible cigarette. The clinic staff will indicate to the subjects when to start and stop each puff. The second session will begin 6 hours following the start of the first session and will consist of *a libitum* use of the e-cigarette product for 5 minutes or use of one cigarette, with no limits on the duration or inter-puff interval for any product. No product use of any kind will be allowed between the sessions.

The clinic staff will document the start and stop time of each session, the number of puffs taken, and reasons for missed puffs during the fixed puffing session. Subjects assigned to an e-cigarette arm will be provided a fully charged battery with a fresh pod for each product use. Pods will be weighed within 24 hours before and after use with the weights documented in grams to 4 decimal places. Products that stop functioning should be replaced as soon as possible, with the failure documented.

6.7.2 Nicotine Pharmacokinetic Blood Sampling

A 4 mL blood sample for plasma nicotine analysis will be drawn into a plastic K₂-EDTA (lavender top) vacutainer tube approximately 5 minutes prior to and at 3, 5, 7, 10, 12, 15, 20, 30, 60, 120 and 180 minutes following the start of each product use episode, with allowable deviation windows of \pm 30 seconds for the samples collected from 3 to 15 minutes, \pm 1 minute for the samples collected from 20 to 60 minutes, and \pm 3 minutes for all other samples.

Approximately 96 mL of blood will be required for the planned PK assessments. Additional blood (typically up to approximately 1 mL) may need to be collected during each time point for the purpose of clearing a blood collection device or line as necessary.

The samples may be kept at room temperature prior to centrifugation, and within 60 minutes from collection will be centrifuged at approximately 1000 to 1300 RCF at ~5°C for approximately 10 minutes. After centrifugation, the plasma will be transferred to two 3.5 mL methanol prewashed polypropylene screw cap tubes, properly labeled, and then stored at -20°C (\pm 10°C) or below (within 120 minutes from collection) until shipped for analysis.

6.7.3 Urge to Smoke Assessment

Urge to smoke will be assessed using a 100 mm VAS (Appendix 11) approximately 10 minutes prior to and within approximately 30 seconds prior to the scheduled blood draws at 5, 10, 15, 30, 60, and 120 minutes following the start of the *ad libitum* product use sessions.

6.8 Other Clinical Considerations

6.8.1 Meals

Meals and snacks will be served at appropriate times during confinement as determined by the clinic, taking into account fasting requirements for endpoint assessments. In addition, subjects will fast for at least 1 hour prior to and 1 hour after the start of each PK product use session. Low-mutagen meals (e.g., no meats cooked at high temperatures [barbecued, grilled, or pan-fried], cured sandwich meats, smoked meats, bacon, salami, and sausages) should be served on days with urine collections for biomarkers. Eggplant is also not to be served during the confinement periods. Subjects will not be allowed to use study products during meals.

Water will be provided as desired during the study, and subjects will be encouraged to maintain their usual hydration habits. Up to one caffeinated beverage per meal may be served.

6.8.2 Reminder Phone Calls

Reminder telephone calls should be made within 24 to 48 hours prior to each test visit to remind them of the date and time of the visits. Subjects should be reminded to maintain their usual smoking/vaping behavior prior to arrival at the clinic. Subjects required to bring their cigarettes to the clinic will also be reminded to bring only unopened packs to check-in for Test Visits 1, 3, and 5.

6.9 Adverse Events

An AE is any untoward medical occurrence associated with the use of a study product, whether or not considered study product-related. An AE can therefore be any unfavorable and unintended sign (including an abnormal laboratory finding), symptom, or disease temporally associated with the use of a study product, whether or not related to the study product.

Details of the monitoring and reporting of AEs will be provided in the Safety Management Plan.

6.9.1 Monitoring

The subjects will be instructed to inform the study physician or staff of any AEs and intercurrent illnesses experienced during the trial. Additionally, a specific inquiry regarding AEs will be conducted at each scheduled clinic visit and during follow-up telephone calls.
The inquiry will be posed in a non-specific manner using open-ended questions so as not to bias the response (e.g., How are you feeling today?).

A subject who has any clinically significant AE or clinically significant abnormal laboratory test value will be evaluated by the Investigator or other monitoring physician and will be treated and/or followed up until the symptoms or values return to normal or acceptable levels (as appropriate in the opinion of the Investigator), or until the subject is lost to follow-up. Where appropriate, medical tests and examinations will be performed to document resolution of the event(s).

6.9.2 Reporting

Events reported prior to use of study products on Day -2 will be documented as baseline signs and symptoms in the medical history. All events occurring after use of study products on Day -2 must be recorded on the eCRF as AEs. Documentation will include the date and time of onset, action taken, outcome (resolved, improved, unchanged, worse, fatal, or unknown/lost to follow-up), duration, relationship to product administration, and severity for each event. AEs will be coded using most current version of the Medical Dictionary for Regulatory Activities (MedDRA)[®] available at

The Investigator will review each event and assess its relationship to product administration as unrelated, unlikely, possibly, probably, or likely.

In addition, each sign or symptom reported will be graded on a 3-point severity scale using mild, moderate, or severe.

6.9.3 Serious Adverse Events

A SAE is any AE that in the view of either the Investigator (or designee) or Sponsor, results in any of the following outcomes: death, a life threatening AE, inpatient hospitalization or prolongation of existing hospitalization, a persistent or significant incapacity or substantial disruption of the ability to conduct normal life functions, or a congenital anomaly/birth defect. Important medical events that may not result in death, be life threatening, or require hospitalization may be considered serious when, based upon appropriate medical judgment, they may jeopardize the subject and may require medical or surgical intervention to prevent one of the outcomes listed in the above definition.

Life threatening is defined as an AE that in the view of the Investigator (or designee) or Sponsor, its occurrence places the subject at immediate risk of death. It does not include an AE that, had it occurred in a more severe form, might have caused death.

Unexpected is defined as an AE that is not consistent with the known risk information associated with the study product.

All SAEs, whether or not considered study-related, must be reported by telephone and by fax or e-mail to the Sponsor within 24 hours of the site's learning of the SAE or, at the latest, on the following workday. The Sponsor's representative to contact about this study is provided

in the list of study contacts. The Investigator must also inform the IRB, in compliance with GCP reporting guidelines, and the site monitor of any SAE.

6.10 Pregnancy

A positive pregnancy test prior to use of study products on Day -2 will result in the subject failing screening. A positive pregnancy test thereafter will be documented by the Investigator on the pregnancy form and will be documented as a protocol deviation. The Investigator or designee will discontinue the pregnant subject from the study and will advise her to seek prenatal care and counseling from her primary care provider. Pregnancy itself is not an AE.

The clinic staff will request the pregnant subject to notify the site of the outcome of the pregnancy (i.e., birth, loss, or termination). To help ensure this, the clinic staff will follow up with the subject until the end of pregnancy, if in compliance with the site's standard operating procedures (SOPs) and with the subject's consent. This request and the subject's response will be documented in the subject's source document.

6.11 Smoking Cessation Information

At screening and prior to discharge from the study (or upon early termination) all subjects will be advised that to reduce the health effects of smoking, the best thing to do is to quit. Subjects will be referred to the Center for Disease Control and Prevention website for quit strategies (https://www.cdc.gov/tobacco/campaign/tips/quit-smoking) and will be encouraged to contact a qualified medical professional for additional advice on smoking cessation.

7. DATA ANALYSIS

Data will be handled and processed according to SOPs, which are written based on the principles of GCP. A brief description of the statistical analysis is included below, detailed methodology for all summary and statistical analyses of the data collected in this trial will be documented in a statistical analysis plan (SAP) prepared by **Source** and agreed upon by the Sponsor. The SAP may modify the plans outlined in the protocol; however, any major modifications of the primary endpoints and/or their analysis will also be reflected in a protocol amendment. If deemed appropriate, additional statistical analyses other than those described in this section may be performed and included in the plan.

7.1 Sample Size Estimation

This study is prospectively powered to find significant decreases in the primary BoE in subjects who switch to my bluTM e-cigarettes for 28 days.

Exclusive use of blu products during a 5-day in-clinic period was previously shown to reduce the primary BoE to be assessed in this study by $\sim 60\%$ to $\sim 95\%$ (O²Connell et al., 2016). In the same study, reducing cigarette consumption by $\sim 30\%$ of that during the baseline period resulted in $\sim 13\%$ to $\sim 27\%$ reductions. However, no published data are available for the current test products, or similar e-cigarette products, over a longer use period from which a sample size may be estimated for this study. Therefore, the sample size estimation was made using Day 30 data from FDA Center of Tobacco Products Docket # FDA-2017-D-3001 (study ZRHM-REXA-08-US) where the applicant assessed similar BoE in subjects who switched to a tobacco heating product or continued to smoke combustible cigarettes during an out-of-clinic product use period.

Based on this previous data, a minimum of 29 subjects per cohort is estimated to be needed to find differences in the Day 28 S-PMA change-from-baseline value equivalent to a 50% reduction in biomarker value compared to the continue-smoking arm using one-sided significance level of 0.0125 (alpha of 0.05 adjusted for multiple comparisons using the Bonferroni method) with a power of at least 80%. Approximately 43 subjects are planned to be randomized into each *my*bluTM e-liquid cohort and 40 subjects into the continue-smoking arm to better ensure that the minimum number complete the Day 28 assessments. The following table provides the power estimate for each of the primary endpoint biomarkers assuming 29 subjects in the ITT population complete the study.

	Test group	Test group	Control group	
	baseline	change-from-baseline	change-from-baseline	
Biomarker	value	SD	SD	Power
COHb (% sat)	6.95	2.28	1.73	>0.9999
NNAL (ng)	340	178	133	0.9623
3-HPMA (µg)	1325	494	500	0.9968
S-PMA (ng)	3348	2370	1512	0.8106

The baseline and change-from-baseline SD values in this table were derived from study ZRHM-REXA-08-US in US FDA Center of Tobacco Products Docket # FDA-2017-D-3001 who had reported Baseline and Day 30 measurements for the listed biomarkers.

Abbreviations: 3-HPMA = 3-hydroxypropylmercapturic acid, COHb = carboxyhemoglobin, NNAL = 4-(methylnitrosamino)-1-(3-pyridyl)-1-butanol, SD = standard deviation, S-PMA = S-phenyl mercapturic acid.

7.2 Analysis Populations

7.2.1 Safety Population

The safety population will include all subjects with at least one reported product use from Day -1.

7.2.2 Intent-to-Treat Population

The ITT population will consist of randomized subjects with at least one documented product-use experience from Day 1, irrespective of their compliance of the product-use to which they were randomized.

7.2.3 **Per-Protocol Population**

The PP population is a subset of the ITT population who meet the requirements below. Separate populations for Product Use Periods 1 and 2 will be established based on data collected during each of those periods.

*my*bluTM and continue-smoking arms

- Have no protocol deviations significantly impacting the integrity of the analysis or interpretation of the individual endpoint under consideration (e.g., compromised urine samples, use of prohibited medications impacting the endpoint)
- Have a daily product use response rate of at least 70% during the product use period
- Have a positive urine cotinine test at each scheduled assessment

mybluTM arm

- Self-report reducing cigarette consumption by at least 90% of that reported at baseline
- Have exhaled CO values ≤ 8 ppm at each scheduled post-baseline assessment
- Have post-baseline urine NNAL values reduced by \geq 75% from baseline

7.2.4 Pharmacokinetics Population

The PK population for each product use session will include subjects who used a product and have evaluable PK profiles.

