#### 6.5.3 Plasma Nicotine Pharmacokinetic Parameters

The appropriate noncompartmental PK parameters will be calculated for each product use episode (controlled and *ad libitum*) from the baseline adjusted plasma nicotine concentration-time data using Phoenix® WinNonlin® Version 7.0 or higher. Actual sample times will be used in the calculations of the PK parameters. The calculation of the actual time for nicotine will be in respect to the start of product use episodes on Day 1 for the JUUL® and continue-smoking arms, and on Day 5 for the *my*bluTM arm. All PK parameters included in the protocol are listed in Table 6.1 below, and are defined as appropriate for study design.

Table 6.1. Noncompartmental Pharmacokinetic Parameters to be Calculated (Baseline Adjusted)

Label to be Used in the Text, Tables and Figures	Definition	Method of Determination
AUC0-t	Area under the nicotine concentration-time curve from time 0 (defined as the start of product use) to 180 minutes (or the last quantifiable concentration during the interval)	Calculated using the Linear Trapezoidal with Linear Interpolation Method
Cmax	Maximum measured plasma concentration over the duration of the measurement interval	Taken directly from bioanalytical data
Tmax	Time to reach the maximum measured plasma concentration over the duration of the measurement interval. If the maximum value occurs at more than one time point, Tmax is defined as the first time point with this value.	Taken from clinical database as the difference in the time of administration and the time of the blood draw which is associated with the Cmax.

Pharmacokinetic parameters will not be calculated for subjects with less than 3 consecutive post-product use time points with quantifiable concentrations. Subjects for whom there are insufficient data to calculate the PK parameters will be included in the concentration tables only and excluded from the descriptive statistics.

For the calculation of the PK parameters, plasma concentrations that are BLQ will be set to one-half of the LLOQ for the calculation of descriptive statistics of unadjusted plasma nicotine concentrations. Baseline adjustments (pre-product use) will be performed for calculation of PK parameters. The values used for all pre-product use adjustments is the plasma nicotine concentration value obtained before the first product use on Day 1-6 and the adjustment will be subject-specific.

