#### 6.5.4 PK Data Summarization and Presentation

All nicotine PK concentrations and/or PK parameters descriptive statistics will be generated using SAS® version 9.4 or higher.

The plasma concentrations of nicotine will be listed and summarized by product, product use episode, and time point for all subjects in the PK Population. Unadjusted and baseline adjusted plasma concentrations of nicotine will be presented with the same level of precision as received from the bioanalytical laboratory. Summary statistics, including number of observations (n), arithmetic mean (Mean), standard deviation (SD), coefficient of variation (CV%), minimum, median, maximum will be calculated for all nominal concentration time points. Excluded subjects will be included in the concentration listings, but will be excluded from the summary statistics and noted as such in the tables. All BLQ values will be presented as "BLQ" in the concentration listings and footnoted accordingly.

Mean and individual concentration-time profiles will be presented on linear and semilog scales. Linear mean plots will be presented with and without SD.

Plasma nicotine PK parameters will be listed and summarized by product, product use episode, and time point for all subjects in the PK Population. Pharmacokinetic parameters will be reported to 3 significant figures for individual parameters, with the exception of Tmax, which will be presented with 2 decimal places. Summary statistics (n, arithmetic mean, geometric mean, SD, CV%, geometric CV% (Geom CV%), minimum, median, maximum), will be calculated for plasma nicotine PK parameters AUC0-t, Cmax, and Tmax. Excluded subjects will be listed in the PK parameter tables, but will be excluded from the summary statistics and noted as such in the tables.

The level of precision for each concentration and PK parameter statistic will be presented as follows:

- minimum/maximum in same precision as in bioanalytical data and/or parameter output,
- mean/geometric mean/median in one more level of precision than minimum/maximum,
- SD in one more level of precision than mean/median,
- n will be presented as an integer, and
- CV% and Geom CV% will be presented to the nearest tenth.

Statistical analyses will be performed using SAS and are described in Section 6.7.

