#### 6.6.2 Urge to Smoke Data Summarization

Data will be listed by subject, product, and day (and time point as applicable) and summarized by product and visit (and time point as applicable).

Descriptive statistics (number of observations, mean, median, standard deviation, minimum, and maximum) will be used for continuous data variables.

Figures may be used to display the data graphically, as applicable. All data summarizations and figures will be generated using the PK Population. Data summarizations and statistical analyses will be performed using SAS procedures. Statistical analyses are described in Section 6.7.

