# Statistical Analyses of Pharmacokinetics (*my*bluTM Products Versus the Continuesmoking arm or JUUL arm)

A linear mixed model ANOVA will be performed on the log-transformed nicotine PK parameters AUC and Cmax from each product use session (PK population). The model will include product arm as a fixed effect. Geometric LSMs will be provided for the PK parameters of Cmax and AUC by product arm. Geometric LSM ratio, 95% confidence intervals of geometric LSM ratio, and p-values will be provided for the product arm comparisons for Cmax and AUC. The comparisons of interest will include each of the *my*bluTM product arms compared to continue-smoking arm or JUUL arm. The above statistical analyses will be performed using the following SAS codes.

```
Proc MIXED data=<>;
Class subject arm;
Model LN_dependent variable = arm/DDFM=KR;
LSMeans arm/pdiff CL alpha=0.05;
Run;
```

Non-parametric analysis (Wilcoxon Rank Sum test) will be performed for the comparisons of  $T_{max}$  between test and reference products.

Similar methods will be used to compare the urge to smoke parameters.

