## **14.2 Biomarker Tables**

Tables 14.2.2.1.1.1, 14.2.2.1.1.2, 14.2.2.1.1.3 and other summary tables for ITT population will be in the following format:

Page 1 of X

Table 14.2.2.1.1.1 Summary of Whole Blood COHb by Study Product and Study Day (ITT Population)

				Product			
Day	Statistic	А	В	С	D	E	F
XXXXX	n	X	X	X	X	X	Х
	Mean	X.X	X.X	X.X	X.X	X.X	X.X
	SD	X.XX	X.XX	X.XX	X.XX	X.XX	X.XX
	CV (%)	XX.X	XX.X	XX.X	XX.X	XX.X	XX.X
	SEM	X.XX	X.XX	X.XX	X.XX	X.XX	X.XX
	Minimum	XX	XX	XX	XX	XX	XX
	Median	X.X	X.X	X.X	X.X	X.X	X.X
	Maximum	XX	XX	XX	XX	XX	XX

Note: Product X: < >

Program: /CAXXXX/sas prg/pksas PROGRAMNAME.SAS DDMMMYYYY HH:MM

Programmer Notes: Footnotes to include under the table, as appropriate: < . = Value missing or not reportable. > The Days will be Day -2 (for some endpoints this may be Day -1), Day 28, and Day 56. For Change from baseline and percent change from baseline, Day -2 will not be presented in the table.

A table should also be presented for PK population for the following biomarkers: NNAL, NNN, 3-HPMA, CEMA, HMPMA, S-PMA; this table shall include Day 3.

Tables 14.2.2.1.1.4, 14.2.2.1.1.5, 14.2.2.1.1.6 and other summary tables for PP population (only for primary biomarkers) will be in the following format:

Page 1 of X

Table 14.2.2.1.1.4 Summary of Whole Blood COHb by Study Product and Study Day (PP Populations)

		PP 2	8/29	PP 56,	/57	
Product	Statistic	Baseline	Day 28	Baseline	Day 28	Day 56
 А	n	X	X	X	X	X
	Mean	X.X	X.X	X.X	X.X	X.X
	SD	X.XX	X.XX	X.XX	X.XX	X.XX
	CV (%)	XX.X	XX.X	XX.X	XX.X	XX.X
	SEM	X.XX	X.XX	X.XX	X.XX	X.XX
	Minimum	XX	XX	XX	XX	XX
	Median	X.X	X.X	X.X	X.X	X.X
	Maximum	XX	XX	XX	XX	XX

\_\_\_\_\_\_

Note: Product X: < >

Program: /CAXXXX/sas prg/pksas PROGRAMNAME.SAS DDMMMYYYY HH:MM

Programmer Notes: Footnotes to include under the table, as appropriate: <. = Value missing or not reportable. > Products B through E will also be presented in the table. For Change from baseline and percent change from baseline, Baseline timepoint will not be presented in the table.

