#### **14.2.6 Questionnaires Tables**

Tables 14.2.6.1.1-2, 14.2.6.3.1-2, 14.2.6.4.1-2, 14.2.6.5.1-2, 14.2.6.5.1-2, 14.2.6.7.1-2, and 14.2.6.8.1-2 will be in the following format:

Table 14.2.6.1.1 Summary of PSCDI or PSECDI Total Score by Study Product and Study Visit (ITT Population)

		Product										
Study Visit	Statistic	A	В	С	D	E	F					
XXXXXXXX	n	Х	Х	Х	Х	Х	X					
	Mean	X.X	X.X	X.X	X.X	X.X	Х.Х					
	SD	X.XX	X.XX	X.XX	X.XX	X.XX	X.XX					
	Minimum	XX	XX	XX	XX	XX	XX					
	Median	X.X	X.X	X.X	X.X	X.X	X.X					
	Maximum	XX	XX	XX	XX	XX	XX					
XXXXXXX	n	Х	X	X	X	X	X					
	Mean	X.X	X.X	X.X	X.X	X.X	X.X					
	SD	X.XX	X.XX	X.XX	X.XX	X.XX	X.XX					
	Minimum	XX	XX	XX	XX	XX	XX					
	Median	X.X	X.X	X.X	X.X	X.X	X.X					
	Maximum	XX	XX	XX	XX	XX	XX					

\_\_\_\_\_\_

Product A =  $myblu^{\text{TM}}$  closed system with CF Cosmic Fog Tobacco Chill flavor, nicotine salt liquid 2.5 % Product B =  $myblu^{\text{TM}}$  closed system with CF Cosmic Fog Tobacco Chill flavor, nicotine salt liquid 4.0%

Product  $C = myblu^m$  closed system with CF Cosmic Fog Honeymoon flavor, nicotine salt liquid 2.5 %

Product D = myblu™ closed system with CF Cosmic Fog Honeymoon flavor, nicotine salt liquid 4.0%

Product E = Subject's usual brand combustible cigarette

Total scoring: 0 - 3 = not dependent, 4 - 8 = low dependence, 9 - 12 = medium dependence, 13+ = high dependence

Program: /AAXXXXX/ECR/sas prg/stsas/tab programname.sas DDMMMYYYY HH:MM

Programmer note: A table should also be presented for PK population; this table shall include Day 3

Clinical Study Report No. CA22747

Programmer note: When there are multiple scores in a questionnaire to be summarized, an additional column for score category will be added to the table.

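### Urge-to-smoke results and the Day 3 biomarker tables are tied to an evaluable nicotine PK profile, which has no bearing on whether those data are valid

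*Protocol*

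**What the plan says.** Protocol 7.2.4 sets membership session by session: "The PK population for each product use session will include subjects who used a product and have evaluable PK profiles". SAP 4.1.4 repeats this and sizes the sub-study at about 120 subjects. Neither document defines evaluable.

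The nearest rule is in SAP 6.5.3: "Pharmacokinetic parameters will not be calculated for subjects with less than 3 consecutive post-product use time points with quantifiable concentrations". Subjects without enough data "will be included in the concentration tables only and excluded from the descriptive statistics". SAP 6.5.4 adds, for concentrations: "Excluded subjects will be included in the concentration listings, but will be excluded from the summary statistics and noted as such in the tables".

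This population is then carried to data that are not nicotine concentrations:

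- **Urge to smoke.** SAP 6.6.2: "All data summarizations and figures will be generated using the PK Population". SAP 6.7.2 extends the PK comparisons to it: "Similar methods will be used to compare the urge to smoke parameters". Tables 14.2.5.1 to 14.2.5.13 and both urge-to-smoke figures are titled PK Population.
- **Day 3 biomarkers.** A programmer note under the biomarker shells in SAP 10.2 reads: "A table should also be presented for PK population for the following biomarkers", and it puts Day 3 in that table. The note under the comparison shell does the same. The ITT biomarker shells cover baseline, Day 28 and Day 56 only.
- **Day 3 questionnaires.** The questionnaire shell note says: "A table should also be presented for PK population; this table shall include Day 3". SAP 6.4.2, however, assigns questionnaire summaries to the ITT population.

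**The concern.** The urge-to-smoke VAS (Protocol 6.7.3) is a self-report. A failed blood draw or a low nicotine concentration says nothing about whether the score is valid. The Day 3–4 urine is complete before the Day 5 PK session (Protocol Table 5), so inclusion of a finished sample depends on a later event. The population is defined per session, and the SAP does not say which session governs Day 3.

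Two things are at stake. First, valid data may be lost from groups of at most 20. Second, if exclusions follow low uptake, inclusion depends on a likely cause of relief. Exclusions that fell mainly on e-cigarette users with low uptake and little relief would raise mean relief for those products relative to the cigarette. Because the study is open-label and evaluable is undefined, membership could also be decided after concentrations have been seen.

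**Working it through.** **1. Planned size.** Four e-liquids × 20 + 20 continue-smoking + 20 JUUL = 120, of whom 100 are also in the main study. This reproduces SAP 4.1.4. The plan gives no power or effect size for urge to smoke or for Day 3.

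**2. Who can be lost.** A subject with no profile at all (failed draws, or withdrawal before Day 5) cannot have an evaluable one, so that loss follows on any reading. For a subject whose profile is mostly below the limit of quantitation, the text does not settle the matter.

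**3. How many low absorbers are plausible.** The documents give no quantitation limit (LLOQ), so a range is assumed. Inputs are the earlier myblu study's 10-puff Cmax (Protocol 1.2), as geometric mean GM and geometric CV: 25 mg salt 7.576 ng/mL, 80.6%; 40 mg salt 10.27 ng/mL, 83.6%; cigarette 17.81 ng/mL, 49.6%. Cmax is assumed log-normal, with σ = √ln(1 + CV²) and P(Cmax < c) = Φ[(ln c − ln GM)/σ]. Cmax below 2 × LLOQ serves as a crude proxy for failing the three-sample rule.

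Example, 25 mg at LLOQ 2: σ = √ln(1 + 0.806²) = 0.7075; P(Cmax < 4) = Φ[(1.386 − 2.025)/0.7075] = 0.183; × 20 = 3.7.

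| Assumed LLOQ (ng/mL) | 25 mg, Cmax < LLOQ | 25 mg, Cmax < 2 × LLOQ | 40 mg, Cmax < LLOQ | 40 mg, Cmax < 2 × LLOQ |
|---|---|---|---|---|
| 0.2 | 0.00 | 0.00 | 0.00 | 0.00 |
| 0.5 | 0.00 | 0.04 | 0.00 | 0.01 |
| 1 | 0.04 | 0.6 | 0.01 | 0.25 |
| 2 | 0.6 | 3.7 | 0.25 | 2.0 |

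(Entries are expected subjects out of 20.) For the cigarette the proxy gives about 0.01 of 20 at LLOQ 2. Any low-uptake loss would therefore fall on myblu rather than the cigarette, but it is close to nil at an LLOQ of 0.5 or below.

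**4. Effect on mean relief if k of 20 are excluded.** Let retained subjects have mean relief m.

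- Excluded subjects with zero relief: full mean = m(20 − k)/20, so overstatement = 20/(20 − k) − 1.
- Excluded subjects with half relief: full mean = m(20 − k/2)/20, so overstatement = 20/(20 − k/2) − 1.
- Excluded subjects typical: no bias; standard error rises by √(20/(20 − k)) − 1.

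| k | Zero relief | Half relief | SE increase if typical |
|---|---|---|---|
| 0 | 0 | 0 | 0 |
| 1 | 5.3% | 2.6% | 2.6% |
| 2 | 11.1% | 5.3% | 5.4% |
| 3 | 17.6% | 8.1% | 8.5% |

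**The case against.** A reader might infer that users who absorb little nicotine are removed and that relief is therefore overstated. The documents do not establish this. The three-sample rule governs calculation of PK parameters, not population membership. Subjects who fail it stay in concentration tables that are themselves titled PK Population, and SAP 4.1.4 sizes the population as the whole sub-study. Eleven post-use samples are drawn per session and only three in a row must be quantifiable. The ad libitum session starts 6 hours, or three assumed half-lives, after the morning session, so about 12.5% of the morning nicotine remains. That helps if the rule is applied to unadjusted values, which the SAP does not say. All of this stands against a claim of demonstrated bias.

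A reader might also point to the earlier study, where PK results exist for 13 to 15 of 15 subjects by product. That is not evidence of PK exclusions: the subjective-effects table for the Safety Population shows the same n for each product.

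Nor are the Day 3 questionnaires shown to be lost. SAP 6.4.2 assigns them to ITT, the titles of Tables 14.2.6.3.1 to 14.2.6.6.1 say ITT by study day, and the shell note asks for a PK-population table in addition. What remains is that Day 3 is named only in that extra table.

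Finally, a common set keeps uptake and urge on the same subjects. That is a fair reason to show such an analysis, but not to make it the only one. Nothing in either document explains why a VAS score or earlier urine should depend on a nicotine profile.

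**Conclusion.** The point holds as a matter of analysis population. Urge-to-smoke results and the Day 3 biomarker tables carry an irrelevant condition, and for Day 3 that condition is set by a later event. Valid data may be lost through failed draws, unquantifiable nicotine or withdrawal before Day 5.

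The bias is conditional. It requires that exclusions occur, that they fall mainly on low-uptake e-cigarette users, and that those users have less relief. Under those assumptions mean relief would be overstated by 5%, 11% or 18% for k = 1, 2 or 3 of 20 at zero relief, and by about half as much at half relief. With k = 0, likely at a low LLOQ, nothing changes. Bias in product contrasts also needs unequal exclusion. The earlier data make that plausible against the cigarette, but the documents give no JUUL uptake data, so the direction against JUUL is unproven. The relief argument does not apply to the Day 3 biomarkers, where the issue is loss of valid samples. These are secondary results; the Day 28 ITT primary analysis is unaffected.

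**What to change.** - Define evaluable in SAP 4.1.4 and apply it to nicotine PK parameters only.
- Analyse urge to smoke in all sub-study subjects who used the product and have a pre-use and at least one post-use VAS in the ad libitum session. Amend SAP 6.6.2, Tables 14.2.5.1 to 14.2.5.13 and the two figures.
- Tabulate Day 3 biomarkers in all sub-study subjects with Day 3–4 urine, and amend both biomarker shell notes.
- Show the PK population as a sensitivity set, with the number excluded reported per product.
- Add a Day 3 column to the ITT tables for the questionnaires given that day, so that SAP 6.4.2 and the questionnaire shell note agree.

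The cost is SAP wording and one more population flag; no new data are needed. The small downside is that n may differ slightly between the PK and urge-to-smoke tables.
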